13.	Taking the Work Forward	. 20
14.	Intellectual Property (IP)	. 20
15.	Costing Schedule	. 21
16.	Funding Arrangements	. 21
17.	References	21

1. Study Synopsis/Profile

Study title	Investigating the tolerability and feasibility of transcutaneous vagus nerve stimulation following aneurysmal subarachnoid haemorrhage				
Study short title	tVNS in aSAH				
Study design	Two-arm randomised controlled trial				
Study participants	Inclusion criteria:				
	 Age >18 Admitted to STH neurosurgery Confirmed aneurysmal SAH on vascular imaging Within 5 days of 'Securing' aneurysm (i.e., successfully coiled or surgically following rupture) 				
	Exclusion criteria:				
	 Current or prior use of a vagus nerve stimulation Symptomatic bradycardia or PPM insertion Complete heart block Implantation of any other electrical stimulator (e.g. DBS) 				
Planned sample size	30 participants (15 in each arm)				
Planned study period	36 months				
Planned recruitment period	24 months				
Study assessments	 Deliver TVNS using the parasym device for 45 minutes twice daily for 5 days following aSAH intervention (coiling or clipping) Pulse width 25ms, frequency device standard (25 Hz), at maximum tolerated intensity, or 				

	20MA for patients who cannot report the maximum tolerated intensity • Clinical follow-up on discharge and at 1 month				
Objectives	s Primary				
•	To establish the tolerability, and feasibility of tVNS in patients following aSAH, including;				
	 Monitor tolerability for tVNS Symptom severity scores of mild or moderate in less than 1/3 of participants able to report symptoms Assess study feasibility recruit >1 patient per month of recruitment >80% of recruited patients completing primary outcome measures 				
	Secondary				
	 Monitor safety criteria for tVNS No SAEs reported to tVNS Unexpected AEs in less than 1/3 of participants Explore clinical outcomes including: rates of clinical or radiological DCI inpatient mortality inpatient length of stay Rate of complications: seizures, hyponatraemia, rebleed, hydrocephalus Outcome measures using questionnaires on discharge and at 1-month Disability assessment: modified Rankin Score, Barthel Index Assess frequency and severity of headache: Likert scale Explore mechanisms of action: Inflammatory markers at baseline and 5 days Explore response to tVNS: 				
	 Near-infrared cerebral spectroscopy Heart rate variability Pupillary reactivity 				

2. Research Questions

Is transcutaneous nerve stimulation a tolerable and feasible intervention to potentially improve clinical outcomes in aneurysmal subarachnoid haemorrhage (aSAH)?

3. Abstract/Summary

Background

Subarachnoid haemorrhage (SAH) is a type of brain bleed, which can be complicated by issues including delayed cerebral ischaemia (DCI) which causes stroke like symptoms, such as weakness, in up to 30% of patients. Current treatments for DCI focus on improving blood supply but fail to address other important factors including reducing inflammation.

Stimulation of a nerve in the neck called the vagus nerve, which can be done through the skin (transcutaneous vagus nerve stimulation, tVNS) is known to relax blood vessels and reduce inflammation and is approved in other conditions such as epilepsy.^{3,4} In animals, vagus nerve stimulation improves survival after aSAH, and is being studied in humans to reduce headaches after aSAH.^{5,6}

There is a theoretical role of tVNS in improving outcome after aSAH. We aim to study whether tVNS is tolerated, and feasible in aSAH.

Methods

This is a single centre, pilot randomised controlled trial (RCT); the participants will receive either tVNS or 'sham' tVNS, twice daily for 45 minutes for 5 days. We will monitor tolerability (symptoms) and feasibility (recruitment rates) for recruited patients. Secondary outcomes will include rates of side effects, complications from SAH, outcomes on discharge and 4 week follow up, and exploration of mechanisms of action and response to tVNS including levels of serum inflammatory markers (IL-1B, IL-4, IL-6, IL-10 and TNFa), functional near infra-red spectroscopy (f-NIRS), heart rate variability (HRV) and pupillary light reactivity (PLR).

Results

Rates of complications, side effects and recruitment will be reported descriptively and we will undertake simple between-group statistical analyses on secondary outcome measures. If proven to be tolerated and feasible, this study will provide the basis for a future larger trial design.

4. Aims of the Study

The aims of the study will be to conduct a pilot RCT to investigate whether tVNS is a tolerable and feasible treatment for acute aSAH. To understand this we will recruit participants who have recently undergone acute securing procedures follow acute aSAH (coiling or clipping of aneurysm) to a 5 day programme of intervention (active tVNS vs sham) and collect outcome data (primary and secondary as per outcomes section). We will evaluate whether pre-defined success criteria are achieved for tolerability and feasibility and explore signals of effect on clinical outcome measures and mechanistic measures. Non-invasive vagal nerve stimulation has not been

studied in the acute period following aSAH outside of the remit of reducing headache. This should offer critical insights as to whether this intervention has potential to take forward to a larger phase 2/3 clinical study.

5. Background

Delayed cerebral ischaemia (DCI) is a multifactorial sequela of aneurysmal subarachnoid haemorrhage (aSAH) which occurs in up to 30% of patients, usually within 14 days of ictus. Diagnosis is by means of clinical and radiological assessment of a new neurological deficit in the absence of other causes. Alongside rebleeding, DCI is the strongest predictor of in-hospital mortality after aSAH and has a significant impact on morbidity.

The pathophysiology of DCI is complex and poorly understood, but emerging evidence supports a multifactorial model which includes arterial vasospasm, inflammatory processes, localised coagulopathy, and failure of cerebral autoregulation – this represents a vasculopathic progress, rather than purely vasospasm. Current management strategies for DCI focus on overcoming vasospasm, primarily by inducing hypertension, although this fails to address other important factors in the disease pathophysiology such as the inflammatory process. Interventions that target a multiple pathophysiological pathways may offer greater clinical benefits.

Several studies are ongoing to address the utility of novel therapeutic targets in DCI. Vagus nerve stimulation (VNS) is known to have vasodilatory and anti-inflammatory effects and is licensed in other conditions including migraine and epilepsy.^{3,4} In animal models, transcutaneous VNS (tVNS) has been found to reduce aneurysm rupture rates and improve survival after aSAH.⁸ Studies are ongoing to establish its efficacy in reducing post-SAH headache.⁵ However, there have been no studies investigating the use of tVNS in delayed cerebral ischaemia.

6. Plan of the Investigation

6.1 Methodology

This is a single centre, pilot, randomised controlled trial. 30 participants who have suffered an aneurysmal subarachnoid haemorrhage and had their aneurysm secured (coiled or clipped successfully).

The intervention will take place for 45 minutes twice a day for 5 days after securing the aneurysm. The placebo group will receive the same intervention, but the device will be in 'sham' mode (i.e. attached to the earlobe).

It is not known whether tVNS is tolerable, and feasible in aSAH, but standard device settings will be used in accordance with a majority of other studies. Similarly, the optimal therapeutic duration is not known – 45 minutes twice a day is a similar usage to other studies. A 5-day course has been chosen because it covers the highest risk period for DCI and is feasible for the research team to deliver.

6.2 Design

This is a single centre pilot, single blind, randomised, placebo – controlled study.

This has been chosen as it will demonstrate feasibility and tolerability, whilst providing early data to indicate whether tVNS may provide benefit in this setting, supporting the development of a larger RCT to establish whether it is a statistically significant benefit.

Patients may be able to tell the different between an activated device and sham (where the device is applied to the earlobe instead of the tragus). However, they will not experience both settings, and we will make no clear distinction of exactly what they should feel.

6.3 Setting

The patients will be inpatients under Neurosurgery at the Royal Hallamshire Hospital. All outcome measures will be collected at recruitment, discharge and 1 month following discharge. They will undergo the TVNS intervention as an inpatient for 5 days.

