6.7 Outcome Measures

Primary Outcome Measures – success criteria:

- Monitor tolerability for tVNS
 - Symptom severity scores of mild or moderate in less than 1/3 of participants able to report symptoms (based on Likert Scale 1-5; 1 representing no issues; 5 representing severe symptoms)
- Assess study feasibility
 - recruit >1 patient per month of recruitment
 - >80% of recruited patients completing primary outcome measures at 4 weeks follow up

These outcome measures will be collected during the participants inpatient stay over the intervention period using a data collection proforma (appendix) and taken from recruitment records kept contemporaneously. Safety assessment of SAEs / AEs will be collected each intervention day by our research team.

Secondary Outcome Measures:

- Monitor safety criteria for tVNS
 - No SAEs reported to tVNS
 - Unexpected AEs in less than 1/3 of participants
- Explore clinical outcomes including:
 - rates of clinical or radiological DCI (%)
 - inpatient mortality (%)
 - inpatient length of stay (days)
 - rate of complications: seizures, hyponatraemia, rebleed, hydrocephalus (%)
- Outcome measures using questionnaires on discharge and at 1-month
 - Disability assessment: modified Rankin Score, Barthel Index
 - Assess frequency and severity of headache: Likert scale
- Explore mechanisms of action:
 - Inflammatory markers at baseline and 5 days
- o Explore response to tVNS:
 - Near-infrared cerebral spectroscopy
 - Heart rate variability
 - Pupillary reactivity

These will be measured during the inpatient hospital stay up until discharge (Figure 1).

- Outcome measures using questionnaires at on discharge and at 4 week follow-up
 - Disability assessment: modified Rankin Score, Barthel Index
 - Assess frequency and severity of headache: Likert scale (1-10 where 1 is non-existent and 10 is extremely severe)
- Explore mechanisms of action measured at baseline and at the end of intervention (5 days):
 - Inflammatory marker analysis at baseline and 5 days (IL-1B, IL-6, IL-10, TNFa)
 - Concurrent WCC, CRP and infection will be recorded at these time points as these may confound results
- o Explore response to tVNS:
 - Near-infrared cerebral spectroscopy

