6.10 Study Protocol

Patients (or their representatives if they lack capacity) who are eligible for entry into the will be approached by the treating clinical teams with information about the study. Those who are interested will be given an information sheet and time to consider the study. Those keen to participate will sign a consent form (or assent form for those that lack capacity) and baseline outcome measures will be performed.

Enrolled participants will be issued with a study number and randomised 2:1 (SealedEnvelope Ltd) stratified according to age (<65 and ≥ 65 years). They will then receive either active tVNS stimulation (tragus) or sham (earlobe), twice daily for 45 minutes per session for 5 days. We do not anticipate discharges from hospital earlier than 5 days as this is not routine practice in the neurosurgical unit.

Primary outcome measures of tolerability and feasibility will be collected daily by researchers delivering the intervention, and secondary outcome measures will be collected at the end of intervention or on hospital discharge as detailed in figure 2.

Following discharge from hospital participants will return for follow up clinic assessment at 4 weeks where questionnaire measures of functional recovery and adverse event reporting will be undertaken. After this the participants involvement in the study will be complete.

Figure 2: Study Schedule for Outcome Measures

	Baseline visit	Visit 1	Visit 2	Visit 3	Visit 4	Visit 5 (EOT)	discharge	At 4 weeks
Eligibility screening	Х							
Informed consent	Х							
Randomisation	Х							
Socio- demographic data	X							
Clinical data collection	X						X	
Questionnaires: Disability - mRS, BI, headache likert scale	X						X	X
Reporting of side effects, adverse events and tolerability		X	X	X	X		X	X
Intervention reporting – settings delivered, duration of intervention		X	X	X	X			
Pupillometry + recording of prescribed eye drops	X					X		
Heart rate variability	X					X		
fNIRS	Х					X		
Monitor blood test results (secondary outcome measures), collection of data on WCC/CRP and infection status	Х	X	X	X	X		X	
Inflammatory marker analysis	X					Х		

EOT = End of treatment; BI = Barthel Index;

fNIRS = Functional near infra-red spectroscopy

7. Data Management

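### Disability and headache are scored only at discharge and about four weeks after it, so time since randomisation at assessment moves one-for-one with length of stay

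*Protocol*

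**What the plan says.** Four places in the protocol set the timing of the disability and headache scores.

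- Section 6.3 fixes the anchor: "All outcome measures will be collected at recruitment, discharge and 1 month following discharge".
- Section 6.10 repeats it: "Following discharge from hospital participants will return for follow up clinic assessment at 4 weeks".
- The synopsis (section 1) has "Clinical follow-up on discharge and at 1 month", and section 6.7 has "Outcome measures using questionnaires at on discharge and at 4 week follow-up". Neither names another starting point.
- Figure 2 marks the questionnaire row (mRS, Barthel Index, headache scale) at baseline, discharge and four weeks only. Pupillometry, heart rate variability, fNIRS and inflammatory markers, by contrast, have a fixed end-of-treatment visit.

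Section 6.7 lists "Disability assessment: modified Rankin Score, Barthel Index" as a secondary outcome. Length of stay in days and "inpatient mortality" are separate secondary outcomes in the same section. On the shortest stay, section 6.10 says "We do not anticipate discharges from hospital earlier than 5 days". No typical or maximum stay is given.

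**The concern.** Discharge happens after randomisation, and time to discharge is one of the quantities the trial compares. When the visit clock starts at discharge, two participants with the same recovery curve but different stays are scored at different points on it.

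If function improves over these weeks, the arm with the shorter stay is scored earlier in recovery and looks relatively worse, and the arm with the longer stay looks relatively better. The discharge score has the same defect, so no post-baseline disability score is free of it.

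At stake is the reading of any between-arm signal on disability or headache. Section 4 says the study will look for such signals, and section 6.2 says the early data should support a larger trial, which might also inherit the schedule.

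**Working it through.** The plan states no figure that depends on visit timing, so there is nothing to reproduce. The check is arithmetic on the schedule.

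**Inputs**
- S = days from randomisation to discharge. Section 6.10 implies a floor of about 5 days. Values above that are assumptions.
- Gap from discharge to the final visit: 28 days (four weeks, sections 6.7 and 6.10, Figure 2) or about 30 days (one month, synopsis and section 6.3).
- N = 30. The synopsis gives 15 per arm; section 6.10 gives 2:1 allocation, which would be 20 and 10.

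**Step 1: day of the final score.** Day = S + 28, or S + 30.

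| S (days) | S + 28 | S + 30 |
|---|---|---|
| 5 | 33 | 35 |
| 14 | 42 | 44 |
| 21 | 49 | 51 |
| 28 | 56 | 58 |
| 42 | 70 | 72 |

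Over an assumed stay of 5 to 42 days, the four-week version runs from day 33 to day 70. The spread is 70 − 33 = 37 days, which equals the spread in stay (42 − 5 = 37). The ratio is 70/33 = 2.1. The choice between four weeks and one month moves every visit by about 2 days, which is minor.

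**Step 2: difference between arms.** Mean assessment day in an arm = mean S + 28. The constant cancels, so

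mean day (active) − mean day (sham) = mean S (active) − mean S (sham).

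A 7-day difference in stay is therefore a 7-day difference in assessment time.

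**Step 3: how large could a chance difference be?** For illustration only, take S as uniform from 5 to 42 days.
- SD = 37/√12 = 10.7 days.
- Standard error of the difference, 15 and 15: 10.7 × √(1/15 + 1/15) = 3.9 days.
- Standard error of the difference, 20 and 10: 10.7 × √(1/20 + 1/10) = 4.1 days.

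Under this assumption, a gap of about 4 days between arms would be unremarkable with no treatment effect on stay. One of about a week lies within two standard errors (2 × 3.9 = 7.8).

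**Step 4: a fixed anchor.** If the visit is due on one day T from randomisation, the due day is T for everyone, the spread is 0 apart from the window, and the between-arm difference in due time is 0 whatever happens to stay.

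**The case against.** The strongest objection is that this is a feasibility pilot. The affected outcomes are secondary. Section 7.2 says the comparisons are not powered and that most data will be reported descriptively. Section 7.1 expects about half the participants to be unable to complete questionnaires and says such measures would then not be carried forward. A bias in an efficacy estimate that the trial does not claim to make matters less than one in a confirmatory trial. That stands, and it limits the weight of the point. It does not remove it, because the protocol still plans between-group comparisons and offers them as a basis for the next trial.

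It can also be said that re-anchoring is not free, which is true and is costed under the fix.

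A reader might infer more than the protocol supports:

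- **That the >80% completion criterion is undermined.** It is a yes/no count of completion (section 6.7). Variable timing does not change what counts as complete, and a participant who dies before the visit would be a non-completer under either anchor.
- **That the anchor is unclear.** The synopsis and the Figure 2 column heading do not restate it, but sections 6.3 and 6.10 do, and no passage names a competing one.
- **That in-hospital deaths are lost.** They are counted under inpatient mortality. They have no post-baseline disability score, but how a death is scored may properly be left to an analysis plan that is not shown.
- **That tVNS is expected to shorten stay, giving bias in a known direction.** The protocol only lists stay among outcomes to explore.
- **That late recruits cannot be followed up.** From 30 June to 31 August 2025 is 62 days, and 62 − 28 = 34. The difficulty therefore needs a last-day recruit with an assumed stay above 34 days, and section 8.1 is a month-level project plan, not a cut-off rule.

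**Conclusion.** The point holds for the exploratory disability and headache comparison. Both post-baseline scores are tied to discharge, so time since randomisation equals stay, or stay plus about four weeks. Any between-arm difference in stay passes unchanged into assessment time: a systematic difference would bias the comparison, and a chance one would distort the result of this small trial.

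The identity between stay and assessment day needs no assumption. The range of day 33 to day 70 rests on an assumed stay of 5 to 42 days, and the 4-day chance imbalance also assumes a uniform distribution. The direction of any distortion depends on how function changes over these weeks and on which arm stays longer; the protocol settles neither.

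The primary tolerability result, collected daily during treatment, is unaffected. This is a change that should be made, not a fault that stops the trial from answering its main question.

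**What to change.** - Time the final mRS, Barthel and headache assessment from randomisation, on the same day for all participants, with a stated window. Choose a day late enough that most will have been discharged, using the unit's own stay data, and state the basis.
- Assess on the ward if the participant is still an inpatient, and in clinic or by telephone otherwise.
- Record a death before that day as mRS 6.
- Keep the discharge scores, labelled as descriptive.
- Use one term (four weeks or one month, not both) and one anchor in the synopsis, sections 6.3, 6.7 and 6.10, and Figure 2.

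**Cost.** This is mainly protocol wording. Some assessments will no longer coincide with the post-discharge clinic, and telephone assessment is a new procedure in a study that funds no additional staff (section 15). Section 7.1 already places researchers on the neurosurgical units during recruitment and intervention, which helps with ward assessments. The four-week visit also carries adverse event reporting. For a participant whose stay exceeds T − 28 days, a visit on day T would end that reporting earlier than now, so it should continue to the later of the fixed visit and the present four-week post-discharge point.

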6.4 Participants

Inclusion criteria:

- Age >18 yrs
- Admitted to STH neurosurgery
- Confirmed aneurysmal SAH on intracranial vascular imaging
- Within 3 days of 'Securing' aneurysm (i.e., successfully endovascularly coiled or surgically clipped following rupture)

Exclusion criteria:

- Current or prior use of a vagus nerve stimulation device
- Symptomatic bradycardia
- Complete heart block
- Presence of other implanted electrical stimulator (e.g. DBS)
- Pregnancy

6.5 Sample Size

A sample size of at least 30 has been chosen based on the number or participants required for the purposes of a feasibility assessment.⁹ It is also a practically feasible number of participants to recruit based on annual admission numbers of patients to the RHH and the timeframe of the recruitment period.

6.6 Recruitment

Potential participants with aSAH will be identified on admission to neurosurgery at RHH and approached about the study by the clinical treating team on the basis of convenience sampling. If they are interested in the study, they will be provided with an information sheet again and the opportunity to discuss the study with a member of the research team. If they are willing to take part in the study written informed consent will be obtained, after a screening consent support tool is used to ensure the patient had adequate comprehension.

Capacity to consent to the study would be determined by the treating clinical team and confirmed by the research team according to the principles of the mental capacity act (MCA, 2005). Where the patient lacks capacity to consent (including sedated/intubate patients), a personal or nominated consultee can provide advice on what they feel the patients' wishes would be if they had capacity. The treating clinical team would

introduce the study to the consultee and an information leaflet given to them. The consultee would then have the option to sign a consent form if they believed the patient would agree to participate. In accordance with the MCA 2005, ongoing consent or assent would be sought from the individual or consultee at each study visit, before any research activity at the that visit is undertaken. Consultees may advise at any point that they believe the person's wishes about participation have changed and they should therefore be withdrawn from the study. Agitated patients will not receive the intervention if they are unable to tolerate it.

